While thoracic epidural catheters confer visceral and somatic analgesia and have long been considered the gold standard for management of postoperative pain following cardiothoracic surgery, there are notable concerns involving systemic heparinization following epidural placement increasing the risk of epidural hematoma, with potentially catastrophic neurologic sequelae, as well as one of the more common side effects of hypotension from sympathetic blockade, which can be deleterious for cardiac patients in the immediate postoperative period^{5,6}. For these reasons, the field of regional anesthesia has progressed to investigating more peripheral targets for nerve blockade that are distant from the neuraxis and more targeted to the specific drivers of surgical pain. Fascial Plane Blocks (FPB) have become a common approach to blocking afferent sensory innervation of the chest wall for patients undergoing cardiothoracic surgery involving sternotomy, including Pectoral (PECS) blocks, Serratus Anterior Plane (SAP) blocks, and Erector Spinae Plane (ESP) blocks^{4,7}. The Pecto-Intercostal Fascial Block (PIFB) is one such approach that anesthetizes the anterior cutaneous branches of the second through the sixth intercostal nerves, which innervate the sternum and overlying soft tissue, by injection of local anesthetic in the fascial plane between the pectorus major and internal intercostal muscles. The PIFB has been demonstrated to reduce postoperative resting and dynamic pain scores, postoperative opioid consumption, time to extubation, duration of intensive care unit (ICU) stay, and incidence of postoperative nausea and vomiting (PONV) in patients following cardiac surgery^{8,9}.

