The purpose of this randomized, triple-blinded, prospective, feasibility study is to compare postoperative analgesia provided by PIFB when performed with local anesthetic solution with or without perineural adjuvants in patients following cardiac surgery involving sternotomy. We hypothesize that the patients receiving PIFB with bupivacaine with epinephrine, clonidine, and dexamethasone will have lower dynamic pain over the first 24 hours compared to those receiving PIFB with just bupivacaine and epinephrine. The primary outcome will be the 24 hour area under the curve (AUC) pain scores, based on patient-reported dynamic NRS pain scores with incentive spirometer (IS) use measured at 6, 12, 18, and 24 hours after block placement in patients that are extubated. We set a minimally clinical important difference (MCID) to be 10% for AUC pain scores with IS use. Secondary outcomes will include patient-reported NRS pain scores at rest at 6, 12, 18, and 24 hours after block placement; cumulative 24 hour opioid consumption; time to first postoperative opioid administration after extubation; time to extubation; duration of ICU admission; incentive spirometry volumes at 6, 12, 18, and 24 hours after block placement;

nausea incidence; vomiting incidence; postoperative delirium incidence; and patient-reported NRS satisfaction with the analgesic regimen.

Risks to Subjects

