The PIFB has been shown to be a safe block, given its superficial target plane between the pectoralis major and internal intercostal muscles. Although the intended location is not intrathoracic, but rather, superficial to it, the relative proximity to the parietal pleura makes pneumothorax a potential risk of the PIFB. The transversus thoracis muscle is deep to the intended fascial plane and constitutes a safe “backstop” in case of needle advancement farther than intended, before arriving at the parietal pleura. The presence of the internal mammary arteries and veins, which reside in the deeper plane between the internal intercostal and transversus thoracis muscles, are also theoretically potentially at risk of needle puncture, although they are easily visualized and avoided during PIFB performance. Another FPB that similarly targets the anterior cutaneous branches of the upper intercostal nerves, called the Transversus Thoracis Plane (TTP) block, entails advancing the needle to this deeper plane, where the internal mammary vessels lie. Given the intrathoracic location of this deeper block, and attendant risks of pneumothorax and internal mammary vessel injury, our institution has opted to avoid TTP block placement, in favor of the PIFB, as the latter is generally regarded as a safer block. To date, there have been no incidences at our institution or in the literature of any identified pneumothorax or internal mammary vessel injury occurring as a result of PIFB placement.

The risks will be minimized by continuous, real-time, in-plane ultrasound guidance of our echogenic block needles only after identifying the correct anatomy, using color Doppler function on our ultrasound machine as appropriate to more readily identify vascular structures and avoid them. Blocks will be performed by anesthesiologists well versed in performance of the PIFB, or by trained anesthesiology residents or fellows directly supervised by them.

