The time of block placement will be documented as the zero hour time point for the purposes of measurements. As described above, to collect data for the primary outcome, research staff will elicit patient-reported NRS pain scores with use of incentive spirometry at 6, 12, 18, and 24 hours post block placement. If patients are not yet extubated at the 6 hour point, they will be excluded from the study as mentioned above. Research staff will also collect data for secondary outcome measures including, but not limited to: eliciting resting NRS pain scores at 6, 12, 18, and 24 hours after block placement; measuring incentive spirometry volumes in triplicate at 6, 12, 18, and 24 hours; measuring the time after extubation to first opioid administration; time to extubation; duration of ICU admission; calculating incidence of nausea and vomiting based on the administration of the antiemetics ondansetron, metoclopramide, prochlorperazine, and promethazine; assessing delirium based on bedside ICU nurse documentation using Confusion Assessment Method in the ICU (CAM-ICU) in the first 24 hours post block placement; and measuring patient-reported NRS satisfaction with the analgesic regimen at the 24 hour point (0 represents completely unsatisfied and 10 represents completely satisfied).

For the NRS pain scores and measurement of incentive spirometer volumes at each 6, 12, 18, and 24 hours interval, there is a grace period of 1 hour. This is to give the research staff/ ICU nurse the flexibility of completing these tasks.

The cumulative 24 hour opioid consumption will be abstracted from the EMR. All opioids will be converted to oral morphine milligram equivalents (OMME) to allow for appropriate comparison using a widely available dose conversion table. These metrics will be accessed, abstracted, de-identified, and analyzed by research personnel who are blinded to group allocation.

There will also be a 30-day post-block phone call follow-up for ongoing opioid use/last use, such as frequency and dosage, and pain levels in their day-to-day activities.

Statistical Analysis

Power Analysis

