Confidentiality will be protected by collecting only the requisite information required to assess the study outcomes, minimizing the collection of any information that could directly identify subjects. Each patient will be assigned a unique study identifier that will appear on the data collection form, and any protected health information that may directly identify the patient corresponding to the unique study identifier will be kept secure with access limited to designated study personnel. Following collection of all data, subject identifying information will be destroyed at the earliest opportunity, consistent with data validation and study design, producing an anonymous data set for analysis. All patient information collected will be kept confidential during recruitment as well as the remainder of the study. All identifying protected health information will be de-identified in the electronic database during data collection, which will be encrypted and secured in the Atrium Health Wake Forest Baptist private servers and only accessible by two-factor authenticated, password-protected computers. Only selected research personnel who are specifically enrolling patients or collecting or analyzing data will have access to the dataset. No reference to any individual participant will appear in reports, presentations, or publications that may arise from this study.

Data and Safety Monitoring

The principal investigators will be responsible for overall monitoring of the data and safety of study participants and will be assisted by other members of the research personnel in the identification of any safety concerns.

Reporting of Unanticipated Problems, Adverse Events, or Deviations

Each participating attending anesthesiologist will report to the principal investigators about any protocol violations, unanticipated problems with the protocol, or adverse events, which will promptly be reported to the IRB and corresponding government agency, if appropriate.

Resources/Citations

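### Beyond nausea, vomiting and delirium, no adverse event is defined, actively solicited or tabulated by arm, and the 30-day call asks nothing about harms

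*Combined protocol and SAP*

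**What the plan says.** The section on reporting of unanticipated problems, adverse events or deviations sets one explicit duty: "Each participating attending anesthesiologist will report to the principal investigators about any protocol violations, unanticipated problems with the protocol, or adverse events". The Data and Safety Monitoring section just before it makes the principal investigators responsible for safety and adds that they "will be assisted by other members of the research personnel in the identification of any safety concerns". Neither section gives an event list, form, grading, schedule or time window.

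The Objectives section includes three harm-type secondary outcomes: "nausea incidence; vomiting incidence; postoperative delirium incidence". Under Measurements, the first two are obtained by "calculating incidence of nausea and vomiting based on the administration of the antiemetics ondansetron, metoclopramide, prochlorperazine, and promethazine", and the third by "assessing delirium based on bedside ICU nurse documentation using Confusion Assessment Method in the ICU (CAM-ICU) in the first 24 hours post block placement". A 24-hour window is stated for delirium. None is stated for nausea and vomiting, and I take the same one.

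Risks to Subjects says that proximity to the pleura "makes pneumothorax a potential risk of the PIFB". It also names internal mammary vessel puncture and local anesthetic systemic toxicity (LAST). The 30-day call described under Measurements covers opioid use and day-to-day pain.

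**The concern.** The arms differ only in the addition of clonidine and dexamethasone (Interventions), so a feasibility trial of this comparison should say something about how well those drugs are tolerated. As written, it can say little. The person with the explicit duty to report places or supervises the block once the skin is closed, before the patient leaves for the ICU. The hours of interest are then observed by ICU and research staff, who have no stated reporting duty of their own.

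The Randomization section lists who is blinded: patients, outcome collectors, surgeons and critical care staff. The anesthesiologist is not on that list. If that person knows the assignment, the threshold for reporting an event could differ between arms.

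The gap may not be recoverable later. Confidentiality and Privacy restricts collection to what the study outcomes need and has identifiers destroyed as early as data validation and study design allow. Events that are not outcomes therefore fall outside planned collection, and a later chart review may be impossible.

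**Working it through.** **What is named, and what is counted**

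| Event | Where it appears | Outcome? | Stated method of capture |
|---|---|---|---|
| Nausea, vomiting | Objectives, Measurements | Yes | Antiemetic given |
| Delirium | Objectives, Measurements | Yes | ICU nurse CAM-ICU, 24 h |
| Pneumothorax | Risks to Subjects | No | General reporting duty only |
| Internal mammary vessel injury | Risks to Subjects | No | General reporting duty only |
| LAST | Risks to Subjects | No | General reporting duty only |
| Adjuvant toxicity (in vitro concern) | Summary/Purpose/Rationale | No | General reporting duty only |
| Haemodynamic or glucose events after the block | Not listed as measures | No | General reporting duty only |
| Any harm up to day 30 | Not in the content of the call | No | General reporting duty only |

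Data Analysis gives t-tests and intervals for continuous outcomes and repeated-measures analysis of variance for serial ones. It names no method for incidence outcomes and no table of adverse events. Selection Criteria and Measurements also remove patients who are still intubated 6 hours after the block. They have received the study drugs, and nothing says that their harms are kept.

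**What 10 per arm can show**

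The only stated figure nearby is the sample size in Power Analysis: 10 per arm, 20 in total. It is not derived from an event rate, so there is no calculation to reproduce. The event rates and capture fractions below are my assumptions.

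1. *Upper limit when no event is seen, with full capture.* Solve (1 − p)^n = 0.025. For n = 10, p = 1 − 0.025^(1/10) = 0.3085, about 31%. For both arms pooled, n = 20, p = 1 − 0.025^(1/20) = 0.168, about 17%.
2. *Chance of at least one event in 10 patients, 1 − (1 − r)^10.* For r = 1%, 5%, 10% and 20% this is 9.6%, 40.1%, 65.1% and 89.3%. Common events would probably be seen; rare ones probably would not.
3. *Effect of incomplete capture.* If a fraction c of events is reported, 0/10 bounds c × r, not r. The limit for r becomes 0.3085/c: 39% at c = 0.8 and 62% at c = 0.5. At c of 0.31 or below it reaches 100%. The plan gives no basis for any value of c, so zero reports set no usable limit.
4. *Would a test help?* With 0/10 in one arm, Fisher's exact two-sided p for k/10 in the other is 2 × C(10,k)/C(20,k). For k = 4 this is 2 × 210/4845 = 0.087; for k = 5 it is 2 × 252/15504 = 0.033. Only very large differences would register, so counts with intervals are the right summary.

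**The case against.** Several stronger readings are tempting, and the documents do not support them.

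- *Only the anesthesiologist reports.* Data and Safety Monitoring gives the principal investigators and research personnel a role. What is missing is a procedure for it.
- *No harm is compared between arms.* Nausea, vomiting and delirium are secondary outcomes of a two-arm trial, and delirium is documented by ICU nurses. Time to extubation and ICU stay would also reflect some harms.
- *Reporting is voluntary, or the operator is known to be unblinded.* Reporting is a stated duty. The operator is merely absent from the list of blinded people, and the plan does not say that the operator's contact with the patient ends at transfer.
- *The protocol names hypotension as a risk of this block.* The phrase "hypotension from sympathetic blockade, which can be deleterious for cardiac patients in the immediate postoperative period" describes thoracic epidurals, as a reason to prefer peripheral blocks.

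Two further objections have weight. The named risks come from the needle and the local anesthetic, which are the same in both arms, so they are unlikely to separate the arms; Risks to Subjects also reports no identified pneumothorax or vessel injury from this block. And in 20 patients even perfect capture is imprecise. Both points limit what the data could show. Neither is a reason to leave the events uncounted, since the drugs that do differ between arms have no dedicated harm measure at all.

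**Conclusion.** The point holds as a gap in active collection and by-arm reporting of harms beyond nausea, vomiting and delirium. It is not an absence of safety oversight, and it does not affect the primary analysis. Following the plan as written would lose comparable harms data that a feasibility trial could supply cheaply.

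In size: with full capture, zero events in an arm would mean a true rate of at most about 31%. Without solicited capture, it would mean nothing definite. This assumes that 10 patients in the arm receive the block and are all followed for harms. Any ascertainment bias from the operator's knowledge of assignment is a possibility, not something the documents establish. The improvement is worth making because it costs little.

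**What to change.** - Prespecify a short event list: pneumothorax; vessel injury or haematoma; LAST; new chest-wall neurologic deficit; and treated haemodynamic and glucose events. The last two are included as possible effects of the added drugs. That is general pharmacological reasoning and not a statement in the protocol.
- Have the blinded research staff who already collect the 6 to 24 hour data record the list, and state its time window.
- Add an adverse-event question to the 30-day call and state that the caller is blinded. The plan does not now say who makes the call.
- Do this for every patient who receives a block, including those excluded at 6 hours because they are still intubated.
- Extend the reporting duty to ICU and research staff, and add these items to the data that may be collected before identifiers are destroyed.
- Report counts by arm, with the number who received a block as denominator and exact 95% intervals. Make no significance test, and state that 0/10 still allows a rate up to about 31%.

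The cost is a few extra fields and some abstraction time, since the record abstraction now specified is for opioid consumption and not for these events. The trial interventions and visit schedule do not change.
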